### **8.3.10. Cognitive Function**

CogState Detection task speed and accuracy, and CogState Pediatric Identification speed and accuracy will be summarized using descriptive statistics for subjects who participated in previous study 1041 and Study A0081106 direct enrollers, overall and by age group (4 to 11 years, 12 to 16 years).

CogState will perform the analysis of the CogState Detection and CogState Pediatric Identification. CogState SAP will be a separate document and developed by CogState.

### **8.3.11. Exposure and Compliance**

Exposure will be calculated as (date of last dose – date of first dose + 1) across the open-label treatment phase and categorized using Pfizer Data Standards.

Compliance will be based on frequency (BID or TID) of dosing recorded on the dosing record and calculated as:

$$\text{Compliance} = (\text{Actual Dosing}/\text{Expected dosing}) \times 100\%.$$

Study medication compliance algorithm:

1. Open-label treatment phase: date of last dose – date of first dose + 1 (excluding taper phase).
2. Actual Dosing over the open-label treatment phase (excluding taper phase): Using the dosing record to determine the doses reported taken: count number of capsules/doses taken per day (capsule or liquid, as relevant) during the open-label treatment phase and add any recorded extra doses or subtract any recorded missed doses.
3. Expected BID dosing over the open-label treatment phase (excluding taper phase): open-label treatment phase duration \*2; adjusting for AM/PM dosing on first and last days of dosing period.
  - Example of BID dosing: If a subject took only PM dose on the first day of dosing and AM on the final day of dosing, subtract two from expected dosing.
  - Expected TID dosing over the open-label treatment phase (excluding taper phase): open-label treatment phase duration \*3 (excluding first and last day of dosing in addition to the taper phase).

Compliance will be calculated and summarized by liquid dosing, capsule dosing and overall across the whole open-label treatment phase (excluding taper phase), and by visit.

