## **5.2. Drug Supplies**

### **5.2.1. Formulation and Packaging**

Study medication will be supplied by Pfizer as capsules of pregabalin (50, 75, 100, 150, 200, 225, and 300 mg), as well as 20 mg/mL solution. The pregabalin liquid oral solution formulation (20 mg/mL) and the pregabalin oral capsules are bioequivalent. The pregabalin capsules are formulated into size #0 gray/gray capsules. All study medication is to be packaged in bottles that are child-resistant.

Pregabalin capsules are composed of pregabalin, lactose monohydrate, cornstarch, and talc encapsulated in opaque hard gelatin capsule shells composed of gelatin and titanium dioxide. Pregabalin oral solution contains a sweetening agent (sucralose) and a flavor (artificial strawberry).

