#### 5.2.4. Compliance

Subjects will take the study medication according to the instructions provided, and should adhere to the dosing schedule as closely as possible, with study medication administered approximately every 12 hr (ie, q12 hours) in subjects  $\geq 4$  years of age or in 3 equally divided doses (ie, q8 hours) in subjects  $<4$  years of age. Compliance will be defined as the percentage of required doses that were ingested. Subjects who are consistently not compliant with the dosing regimen should be evaluated by the Investigator and discussed with the Pfizer clinician for possible discontinuation from the study.

For subjects who begin taking capsules, but can no longer comply with swallowing after starting, parents/caregivers should break open the capsules and sprinkle the study drug into food for ingestion until the next study visit. Sprinkling should only occur when the child is in danger of missing a dose due to inability to swallow the capsules and there is no liquid dose available at that time. All of the food that the capsule has been sprinkled on must be ingested. This should be noted in the Dosing Diaries and dosing log CRFs. At the next study visit, the site should record the days that the study drug was sprinkled, and then switch the subject to the liquid oral solution form of the study drug for the remainder of the study. An unplanned visit may be scheduled to switch from capsules to liquid if necessary.

If the subject regurgitates or spits out the study drug within 15 minutes after either liquid or capsule administration, the subject/parent/caregiver should re-administer the study drug. If more than 15 minutes have elapsed since drug was taken, no additional study drug should be administered until the next scheduled dose. This occurrence should be noted in the Dosing Diaries and dosing log CRFs.

Administration of the liquid oral solution through a nasogastric (NG) feeding tube will be permitted and should be documented accordingly. If a subject has an NG tube that was inserted prior to entry into the study, it should be documented in the subjects' "Medical History". If a subject has an NG tube inserted during the course of the study, it should be documented in the subjects' "Concomitant Treatments" as a non-drug treatment. Specifying whether the NG tube was inserted or removed during the study is important to document.

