### **5.3. Drug Storage and Drug Accountability**

It is the site's responsibility to handle and store the clinical study supplies under secure and locked conditions. Note that pregabalin, is a controlled substance (CV) in the US, and therefore in the US must be stored according to US/Federal Drug Enforcement Agency (DEA) regulations. The US sites will provide a copy of the DEA license, and proper state/local license if applicable, to the Sponsor. For those countries where pregabalin is not a controlled substance, the sites are to comply with their local regulations.

Study medication must be stored at 15-25°C. Access to the stored study medication should be limited to the Investigator, the Study Coordinator, and the Pharmacist (when applicable). The Investigator, or an approved representative, eg, Pharmacist, will ensure that all study medications are stored in a secured area, under recommended storage conditions and in accordance with applicable regulatory requirements. If the study medication is determined to have been stored or delivered outside the outlined temperature range, the information is to be brought to the appropriate study supply personnel for evaluation.

Storage conditions stated in the investigator brochure may be superseded by the label storage.

Study medication will be dispensed under the supervision of investigator site personnel. Each subject will complete a dosing diary and will bring the diary and the medication bottle(s) back to the clinic at each visit. For those subjects who are dispensed capsules, a pill count will be done by the site staff at each visit, and the subject/caregiver will be queried about any missed or extra doses taken. For those subjects who are dispensed liquid oral solution, medication bottles will be weighed by the site staff when dispensed. The bottles will again be weighed when returned at each visit, in order to determine the approximate volume of study medication consumed. The subject/caregiver will be queried about any missed or extra doses taken or any volume discrepancies.

All dispensed study medication bottles will be locally kept available for checks by the study monitor.

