### 4. HYPOTHESES AND DECISION RULES

#### 4.1. Statistical Hypotheses

Not applicable. No formal statistical analysis will be performed.

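### The SAP's compliance formula lets extra doses offset missed ones and drops two days from the TID denominator alone, so it does not give the protocol's percentage of required doses ingested

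*SAP*

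**What the plan says.** Protocol Section 5.2.4 gives the definition: "Compliance will be defined as the percentage of required doses that were ingested". The unit is a required dose.

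SAP Section 8.3.11 turns this into actual dosing divided by expected dosing, times 100%. It opens with "Compliance will be based on frequency (BID or TID) of dosing recorded on the dosing record". The open-label phase runs from first dose to last dose inclusive, without the taper.

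- **Actual dosing**, over that phase: "Using the dosing record to determine the doses reported taken: count number of capsules/doses taken per day", for capsule or liquid as relevant, and then "add any recorded extra doses or subtract any recorded missed doses".
- **Expected dosing, BID**: phase duration times 2, "adjusting for AM/PM dosing on first and last days of dosing period".
- **Expected dosing, TID**: phase duration times 3, with the first and last dosing days left out.

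Results are to be summarised for liquid, for capsules and overall, across the whole phase and by visit. Protocol Section 5.3 describes a dosing diary, pill counts or bottle weights, and a question at each visit: "the subject/caregiver will be queried about any missed or extra doses taken". Protocol Section 5.2.3 does not allow additional doses.

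**The concern.** A percentage of required doses ingested cannot rise because a subject took a dose that was not required. It also should not exceed 100% because numerator and denominator cover different days. The SAP rule permits both.

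Two other features depend on how the wording is read. A count of doses taken already omits the missed ones, so subtracting them again would penalise each miss twice. The numerator may also be a count of capsules, while the denominator is a count of dosing occasions.

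At stake is the accuracy of a descriptive table. The study's only objective is long-term safety and tolerability, and this table tells readers how fully subjects took the drug. A subject with both missed and extra doses could appear perfectly compliant. The youngest subjects, who are on TID dosing, could show figures above 100% for reasons of arithmetic alone.

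**Working it through.** The documents state no compliance result, so there is no figure to reproduce.

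**Inputs**
- 12-month treatment phase, taken as 365 days (Protocol Section 3).
- BID expected doses with full first and last days: E = 2 × 365 = 730 (SAP Section 8.3.11).
- Capsule strengths: "capsules of pregabalin (50, 75, 100, 150, 200, 225, and 300 mg" (Protocol Section 5.2.1).
- Assumptions not in the documents: missed-dose shares of 2%, 5%, 10% and 20%; 36 extra doses; one or two capsules per dose.

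**1. Extra doses in the numerator.** Take 36 missed and 36 extra doses. Protocol definition: (730 − 36)/730 = 694/730 = 95.1%. Under the SAP rule the result depends on the base count:
- Recorded regimen: (730 + 36 − 36)/730 = 100%.
- All doses taken, extras included: base 694 + 36 = 730, then (730 + 36 − 36)/730 = 100%.
- Scheduled doses taken only: base 694, then (694 + 36 − 36)/730 = 95.1%. This agrees with the protocol only because two errors cancel. Without the extras the same subject scores (694 − 36)/730 = 90.1%.

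On all three, extra doses raise the score and offset missed ones.

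**2. TID days.** For D days with every dose taken, actual = 3D and expected = 3(D − 2):
- D = 365: 1095/1089 = 100.6%.
- D = 30: 90/84 = 107.1%.
- D = 8: 24/18 = 133.3%.

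If only one dose falls on each of the first and last days, the 8-day figure is (18 + 2)/18 = 111.1%. Full adherence still exceeds 100%. The BID rule has no such gap, because it adjusts for doses that could not be taken on those days.

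**3. Missed doses (conditional).** Let m be the share missed. If the base is doses taken, the score is (1 − m) − m = 1 − 2m. If the base is the recorded regimen, it is 1 − m, which is the protocol value.

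| Missed (of 730) | Protocol value, or regimen base | Base is doses taken |
|---|---|---|
| 2% (15) | 97.9% | 95.9% |
| 5% (36) | 95.1% | 90.1% |
| 10% (73) | 90.0% | 80.0% |
| 20% (146) | 80.0% | 60.0% |

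**4. Capsules against occasions (conditional).** With k capsules per dose, a capsule count gives k(1 − m). With k = 1 there is no error. With k = 2 (assumed) and 10% missed it gives 180.0%, or 170.0% if missed doses are also subtracted again, against 90.0%.

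Whether k exceeds 1 is unknown. The four adult BID doses (75, 150, 225 and 300 mg) each match one supplied capsule. For pediatric subjects of 30 to 80 kg in 5 kg steps, at four dose levels, there are 44 combinations: 27 match one capsule, 4 match only a two-capsule sum (for example 50 kg at 5.0 mg/kg/day, or 125 mg per dose), 2 fall below 50 mg, and 11 match neither. The documents give no capsule rounding rule.

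**The case against.** The strongest reply concerns the double subtraction. The section's opening sentence bases compliance on the recorded BID or TID frequency, and the protocol has missed and extra doses asked about separately at each visit. On that footing the daily count is the recorded regimen, the exceptions are applied once, and the missed-dose result is exactly the protocol's. The dosing-record form is not in the documents, so neither reading can be proved. This stands: a reader might infer that compliance will certainly be understated, and the documents do not support that.

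The reply on capsules also stands. A reader might infer that capsule compliance will reach 200%, so that capsule and liquid figures differ by artefact. No section says a dose was made of two capsules, every adult level is available as one capsule, and subjects under 30 kg receive liquid only.

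The reply does not reach the other two defects. Treating the base as the recorded regimen leaves extra doses in the numerator. It also leaves the TID denominator two days short of the phase over which actual dosing is counted. A programmer might drop those days from the numerator too, but the SAP does not say to.

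On weight, compliance is not a listed endpoint, there is no per-protocol set, and the SAP states "No formal statistical analysis will be performed". That limits the consequence.

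**Conclusion.** The concern holds in limited form. As written, SAP Section 8.3.11 does not give the percentage of required doses ingested.

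- **Whichever base count is meant**, extra doses offset missed ones. The 36-and-36 example scores 100% instead of 95.1% if the base is the recorded regimen or all doses taken.
- **For TID subjects**, actual dosing as defined covers two more days than expected dosing. The excess is negligible over a full year (100.6%) and large for short exposure (133.3% over 8 days, with full first and last days).
- **Conditionally**, missed doses are subtracted twice, an understatement of about m percentage points when m percent are missed. The error is zero if the base is the recorded regimen.
- **Conditionally**, a capsule count inflates compliance, but only where a dose takes more than one capsule, which is an assumption.

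It would go too far to say that compliance is certainly wrong in both directions. The severity is minor: the summary is descriptive and feeds no test, analysis set or sample size.

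**What to change.** Amend SAP Section 8.3.11 as follows.

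1. Define Actual Dosing as the number of required dosing occasions recorded as taken, for capsule and liquid alike. However many capsules make up a dose, it counts as one occasion.
2. Account for missed doses once, and state whether the starting count is the recorded regimen or the doses reported taken.
3. Keep extra doses out of the numerator and report them separately.
4. Count Actual and Expected over the same days for BID and TID, with the same first- and last-day adjustment, and say how this works within visit intervals.

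The cost is a few sentences in the SAP and a programming change. No new data collection appears necessary, since the protocol already provides for dosing diaries and for questions about missed and extra doses.

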### **Study Treatments:**

A0081106 study medication will be provided as pregabalin liquid oral solution or oral capsules. Subjects <4 years of age at Visit 1 or who are enrolling from A0081042 will receive study medication 3 times daily (TID) in equally divided doses. Subjects who are  $\geq 4$  years of age at Visit 1 will receive study medication twice daily (BID) in equally divided doses.

- All eligible pediatric subjects 1 month to 16 years and 11 months of age will take pregabalin in Study A0081106 at a dosage according to their body weight:
  - Pediatric subjects weighing  $\geq 30$  kg will begin pregabalin dosing at 2.5 mg/kg/day (maximum 150 mg/day). Subjects will remain at the starting dose for 8 days until Visit 2. Thereafter, dosing will be flexible based on individual seizure response and tolerability. Pediatric subjects may have their dose adjusted up or down at clinic visits in increments of no more than 2.5 mg/kg/day (maximum 150 mg/day) to daily dose levels of 5.0 (maximum 300 mg/day), 7.5 (maximum 450 mg/day), or 10.0 mg/kg/day (maximum 600 mg/day).
  - Pediatric subjects with body weight <30 kg will begin pregabalin dosing at 3.5 mg/kg/day until Visit 2. Thereafter, dosing will be flexible based on individual seizure response and tolerability. Pediatric subjects may have their dose adjusted up or down at clinic visits in increments of no more than 3.5 mg/kg/day to daily dose levels of 7.0, 10.5, or 14.0 mg/kg/day. This 40% higher dose per kg in pediatric subjects with body weight <30 kg is needed to achieve exposures similar to those of adults or pediatric subjects weighing  $\geq 30$  kg.
- All eligible adult subjects 17 to 65 years of age will begin dosing of pregabalin in Study A0081106 at the level of 150 mg/day. Subjects will remain at this dose for 8 days until Visit 2. Thereafter, dosing will be flexible based on individual seizure response and tolerability. Adult subjects may have their dose adjusted up or down at

clinic visits in increments of no more than 150 mg/day to dose levels of 300, 450, or 600 mg/day.

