- Perform urine pregnancy test for female subjects who are menarchal. If the results of the urine pregnancy test are positive, the subject will not be eligible for study participation.
- Collect blood and urine specimens for clinical laboratory assessments. If it is not feasible to obtain a urine sample then no urine sample will be required.

**Note:** In the event that the subject has an exclusionary abnormal screening laboratory value (see [Exclusion Criteria 5](#)) the laboratory test should be repeated. If the repeated test is still abnormal, the subject should be withdrawn from the study at Visit 2. In the event that the subject has an abnormal laboratory value that the investigator determines is significant and exclusionary, the subject should be contacted to stop taking study medication and return to the clinic for an early termination visit.

- Administer the MINI-KID and C-SSRS Lifetime or Child Behavioral Checklist (CBCL) as appropriate for subject's age. If CBCL is administered, scores must be obtained as soon as possible. If positive scores are obtained on the CBCL or CSSRS, a mental health risk assessment must be performed by a qualified mental health professional prior to randomization.

- Assign subject number and dispense study medication via tele-randomization system.
- For direct-enrolling subjects that will receive liquid solution, train parents on dosing administration and demonstrate use of oral syringe/bottles. Have subject and/or child's parents/legally acceptable representative practice dosing in office to verify comprehension of dosing instructions.
- Administer first dose of study medication in office.

Note: all screening procedures must be completed before subject is administered the first dose of study medication. All eligibility criteria should be confirmed prior to, or on Visit 2. If a subject is not deemed eligible, subject should be notified by phone to discontinue study medication, and should come back for an Early Termination visit as soon as possible.

- Dispense subject daily seizure and dosing diary and train subject and/or child's parents/legally acceptable representative on its use and completion.

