## 5. ANALYSIS SETS

### 5.1. Full Analysis Set (Safety Population)

*The primary analysis set will be the Safety population which will include subjects who took at least one dose of the study medication in this study.*

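### Expected TID doses leave out the first and last dosing days while actual doses include them, so full adherence scores above 100%, most visibly in Week 1 and in early discontinuers

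*SAP*

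**What the plan says.** Protocol Section 5.2.4 sets the meaning of the measure: "Compliance will be defined as the percentage of required doses that were ingested". SAP Section 8.3.11 turns this into actual divided by expected dosing, times 100%.

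- **Phase length.** Last dose date minus first dose date plus 1, without the taper. Both end days count.
- **Actual dosing.** The instruction is to "count number of capsules/doses taken per day (capsule or liquid, as relevant) during the open-label treatment phase", then add recorded extra doses or subtract recorded missed ones. Only the taper is left out.
- **Expected, BID.** Phase length times 2, "adjusting for AM/PM dosing on first and last days of dosing period". A worked example subtracts two when one dose was taken on each end day.
- **Expected, TID.** Phase length times 3, "excluding first and last day of dosing in addition to the taper phase".
- **Reporting.** By liquid, capsule and "overall across the whole open-label treatment phase (excluding taper phase), and by visit".

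TID applies to subjects under 4 years at Visit 1 or those "who are enrolling from A0081042 will receive study medication 3 times daily (TID) in equally divided doses" (Protocol Summary, Study Treatments).

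**The concern.** The TID numerator and denominator cover different days. Doses taken on the first and last days enter Actual but have no counterpart in Expected, so a child who takes exactly what was required cannot score 100%. The BID rule does not have this fault.

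This affects how the table is read. Because recorded extra doses are added to Actual, and Protocol Section 5.2.3 forbids double-dosing, a value above 100% ought to signal extra dosing. Under the TID rule it is also what full adherence looks like, and a score of 100% can hide missed doses.

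Two further gaps follow. The SAP does not say whether, for by-visit values, the exclusion applies once per subject or to every visit interval. It also has no rule for very short exposures, which the protocol foresees. A direct enroller takes the first dose at Visit 1B, eligibility may be confirmed as late as Visit 2, and "If a subject is not deemed eligible, subject should be notified by phone to discontinue study medication". One dose is enough to stay in the "Safety population which will include subjects who took at least one dose of the study medication in this study" (SAP Section 5.1).

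**Working it through.** **Inputs.** D is the phase length in days, both ends included (SAP 8.3.11). Visit 2 is Day 8 ±1 and Visit 8 is Day 365 ±7 (Protocol 6.3 and 6.15). Let f and l be the TID doses on the first and last day. The documents give no figure for either, so 1 to 3 each is an assumption.

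**The SAP's BID example first.** With one dose on each end day, Actual = 1 + 2(D − 2) + 1 and Expected = 2D − 2. At D = 365 this is 728/728, and at D = 8 it is 14/14. Full adherence gives exactly 100%.

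**TID as written, whole phase, full adherence.** Expected = 3(D − 2); Actual = 3(D − 2) + f + l, so the excess is 2 to 6 doses whatever the duration.

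| D (days) | Expected | Actual | Score |
|---|---|---|---|
| 365 | 1089 | 1091–1095 | 100.2–100.6% |
| 90 | 264 | 266–270 | 100.8–102.3% |
| 30 | 84 | 86–90 | 102.4–107.1% |
| 14 | 36 | 38–42 | 105.6–116.7% |
| 8 | 18 | 20–24 | 111.1–133.3% |
| 3 | 3 | 5–9 | 166.7–300% |
| 2 | 0 | 2–6 | not calculable |
| 1 | −3 by the formula; 0 if read as no day remaining | 1–3 | not calculable |

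**By visit, continuing subject, exclusion applied once.** Only the first dosing day falls in Week 1.

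- Week 1, 8 days: Expected = 3 × 7 = 21; Actual = 21 + f = 22 to 24. The scores are 104.8%, 109.5% and 114.3% for f = 1, 2 and 3.
- Visit window: 7 days gives 19–21 over 18 = 105.6–116.7%; 9 days gives 25–27 over 24 = 104.2–112.5%.
- Last interval, Days 270 to 365 inclusive (96 days): Expected = 3 × 95 = 285; Actual = 286 to 288, so 100.4–101.1%. Assigning Day 270 to the previous interval gives 283–285 over 282, the same after rounding.

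**By visit, exclusion applied to both ends of each interval.** An 8-day Week 1 gives 20–24 over 18 = 111.1–133.3%.

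**What a Week 1 score of 100% hides (exclusion applied once).** It means 21 doses taken of 22 to 24 due, so true compliance is 21/24 = 87.5% to 21/22 = 95.5%.

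**Check of the remedy.** With f and l now the doses due on the end days, Expected = 3D − (3 − f) − (3 − l) = 3(D − 2) + f + l. This equals Actual under full adherence, so the score is 100% for any D of 2 or more. For a one-day exposure the single day is adjusted once: 3 − (3 − f) = f, again 100%.

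**The case against.** The strongest reply is that nothing hangs on this number. Compliance is not a listed endpoint, no per-protocol set is planned, there is no inference, and discontinuation for non-compliance is a judgement by the investigator and sponsor under Protocol 5.2.4. All of that stands, and it limits the importance of the point.

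Three doses on Day 1 are also unlikely: the first dose follows the Visit 1 procedures, and dosing is about every 8 hours. With 1 or 2 doses that day, Week 1 is 104.8–109.5%, a Week 1 score of 100% means true compliance of 21/23 = 91.3% to 95.5%, and the 365-day maximum is 1094/1089 = 100.5%. The upper ends above are therefore bounds, not expected values. The documents also give no frequency for exposures of a few days. The early-stop route cited covers direct enrollers only, and of those only children under 4 years are on TID.

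The author may have meant to drop the same two days from Actual, which would remove the excess. The text does not say so, although it states the taper exclusion on both sides of the ratio. Even on that reading, one- and two-day exposures remain undefined. A programmer would probably set those ratios to missing, but the SAP gives no such rule.

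**Conclusion.** The point holds. As written, the TID rule puts full adherence above 100% at every exposure of three days or more and gives no usable value at one or two days. This contradicts the protocol's definition of compliance.

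The excess is at most about 0.6 percentage points over a year, which is negligible for completers. It is visible in the Week 1 row, at about 105–114% with the exclusion applied once and an 8-day interval, and in subjects who stop early. All ranges rest on the assumed 1 to 3 doses per end day.

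The affected output is the descriptive compliance summary for TID subjects, and the liquid and overall rows in which they are pooled with BID children. Exposure, site-level compliance checks and the listed endpoints are untouched. It should be corrected because the rule is wrong as written and leaves two programmers free to produce different by-visit tables.

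**What to change.** Replace the TID bullet in SAP Section 8.3.11 with: *Expected TID dosing = open-label treatment phase duration × 3, minus the doses not due on the first and last dosing days (adjusted once if these are the same day).* This follows the BID end-day adjustment. The BID example is worded by doses taken; wording the TID rule by doses due means that an end-day dose that was due but missed still counts as missed.

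Add: *For by-visit compliance, apply the first-day adjustment only to the interval containing the first dose and the last-day adjustment only to the interval containing the last dose; each calendar day belongs to one interval.*

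If the dosing record does not show which TID doses were due on those days, exclude both days from Actual as well as Expected and report exposures of one or two days as not calculable.

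The cost is two sentences in the SAP and a small programming change. The preferred rule needs dose-level detail on the end days. The fallback needs no extra data but leaves the shortest exposures without a value. TID compliance will look slightly less favourable.
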